7 STUDY SCHEDULE

Prior to any of the following actions, practices will be randomized and EMR changes will be finalized.

Refer to **Appendix A** for the Schedule of Events for providers and parents/caregivers.

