4.1 Study participants

Subjects will be pediatric providers (Pediatricians/Nurse Practitioners) and parent/caregivers and their 3-6 year old children from 18 primary care practices located in Ashtabula, Cuyahoga, Geauga, Lorain, Medina, and Portage counties in Ohio (see Table 4.1.1 below). One additional practice not included in the table, Premier Pediatrics, has also agreed to participate and will be included if needed to replace a practice. The majority of the practices are in Cuyahoga County (67%) and the remaining 33% are in surrounding counties in NE Ohio. All practices serve $\geq 20\%$ Medicaid eligible children (9 practices with 20-40% and 9 practices with $> 40\%$ Medicaid-eligible children) and are from the Rainbow Care Connection (RCC). The study is offered to all pediatricians/nurse practitioners in the recruited practices and will be offered to all eligible caregivers and their children excluding those with serious medical or behavioral conditions which would preclude them from participating in the dental screening. All provider and parent participants meeting the eligibility criteria will be enrolled in the study upon signing the consent form.

Table 4.1.1 Practice Information

Practice/Site	# Pediatricians	# Nurse Practitioners	Medicaid Patients (age 3-6)	Medicaid Patients w/WCV (age 3-6)	% Medicaid	County
Ashtabula Pediatrics	1	2	592	448	63%	Ashtabula
Chardon Pediatrics	4	1	387	267	34%	Geauga
Elyria Pediatric Care	3	0	205	168	33%	Lorain
Healthy Kids Pediatrics	1	1	121	95	31%	Portage
[name]	1	0	344	340	80%	Cuyahoga
Medina Pediatrics	4	2	338	250	23%	Medina
NEON	5	0	1856	357	80%	Cuyahoga
Otis Moss	2	0	297	233	82%	Cuyahoga
Pediatric and Adolescent Health Professionals	3	0	157	118	22%	Cuyahoga
Pediatric Partners of Cleveland	2	0	209	165	40%	Cuyahoga
Pediatric Services - Parma	8	0	740	588	30%	Cuyahoga
Pediatriccenter – Garfield	2	0	561	384	24%	Cuyahoga
Rainbow Ambulatory Clinic	4	0	2728	2361	86%	Cuyahoga
Rainbow Euclid Pediatrics	1	0	246	186	68%	Cuyahoga
Suburban Pediatrics - Shaker	7	0	408	335	23%	Cuyahoga
University Premier Pediatricians – Euclid	4	1	504	418	49%	Cuyahoga
UH Westshore Primary Care **	4	0	424	185	45%	Cuyahoga
University Pediatrics of Lorain	4	0	653	523	61%	Lorain
Totals	60	7	10,302	7,421		

Practice information data captured 1/1/2016 through 12/31/2016.

**Data captured 1/1/2017 through 5/31/2017

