5.3 Strategies for Recruitment and Retention

Practices:

During the pilot study phase, Medical Directors from the 26 RCC practices were invited to participate in an informational webinar led by the PI and a Co-Investigator (Medical Director of the RCC) to learn more about the opportunity for their practice to participate in the study. The PI, Project Manager and Study Coordinator then met with interested providers at practices which met the inclusion criteria. The 18 practices which met the inclusion criteria have provided letters of support indicating their commitment to participation. One practice will serve as a backup practice and has also given a letter of support.

Retention strategies for the practices will include regular contact between the study staff and practice staff to ensure any issues which may arise are addressed immediately, and tailoring study logistics based on practice flow as learned from our two pilot practices.

Practices also receive compensation for facility use for the trainings, for research staff being present at the practices to complete study visits, and for the structured interviews and debriefing sessions.

Providers:

During the pilot study phase, all pediatricians and nurse practitioners of the 18 practices were invited to attend the informational meetings which took place at their individual practices. The PI, Project Manager and Study Coordinator briefed the providers regarding the study goals and logistics. A total of 67 providers from the 18 practices to be randomized who met the inclusion criteria will participate in the main trial. An additional information session for providers will be held at each practice prior to the start of the main trial. At this time, informed consent will be obtained from each pediatrician/nurse practitioner participant.

Retention strategies for providers include Continuing Medical Education (CME) credits for didactic OH education and Maintenance of Certification (MOC) credits for quality improvement initiatives. Twenty five (25) MOC credits have been approved by the American Academy of Pediatrics (AAP) for physicians participating in this dental project. The study staff will maintain regular contact with providers to address any concern or issue that may arise.

CME credits will also be available for providers upon completion of briefing seminar.

Parent/caregivers:

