7.1 Provider

7.1.1 Baseline Visit: WCV #1

Before WCV #1 (T₋₁: Day -30 to -1)

- Review the written consent form with the provider; study staff signs the consent form acknowledging that informed consent was reviewed and provider signs acknowledging consent was obtained (Appendix C: Consent forms).
- Provide OH didactic education and skills training for pediatricians/nurse practitioners to communicate core OH facts (importance of baby teeth, chronicity of caries, dental visits) to parents/caregivers (Appendix D: Provider training) or AAP based didactic training, based on study arm.
- Administer pre- and post-tests to pediatricians/nurse practitioners before and after the OH didactic education session (Appendix E: Questionnaires & forms).

At WCV #1 (T₀: Day 0)

- Provider delivers oral health facts, based on study arm.
- Provider documents OH in EMR, based on study arm.

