7.2.5 Parent/Caregiver and Child Unscheduled/Missed Visit

Unscheduled visits for parent/caregiver and child may occur if an enrolled child could not complete the oral health portion during the WCV. But, this is unlikely to happen due to the short amount time required for the oral health activities. Another possibility would be if a child is scheduled by the practice for a well child visit much sooner or later than the visit window. In these cases, study data would be collected per guidelines outlined in the MOP, but the time length between visits will be accounted for in the analysis stage.

Other instances of unscheduled visits at follow-up, i.e. WCV2 or WCV3, may occur if a well child visit is missed by project staff (for example, a child comes in for a sick visit near the time a well child visit is due and the provider completes the well visit also) or another non-participating provider at the practice is scheduled to see the child for a well child visit. In these cases, the ICDAS, A2, A3 and B1 questionnaires will be completed when possible, either in person, by mail or through a link sent via text or e-mail to the parent/caregiver. The B2 follow-up will be completed as planned. In extreme situations, if we have missed the WCV2 or WCV3 and the child is scheduled to come in to see the enrolled provider for follow-up for a problematic issue within 3 months of the missed well child visit, we will arrange to complete the study visit at the follow-up visit. This determination will be made on a case-by-case basis. Arrangements will be made to have the parent/caregiver bring the child to the Dental Research Building for completion of the ICDAS dental screening. Also, due to scheduling irregularities in the part of the parent/caregiver, every child may not be scheduled for an annual WCV. In cases such as this, the parent/caregiver-child dyad may remain enrolled in the study and be seen for completion of 3 consecutive WCV's regardless of their timing. The time length between visits will be accounted for in the analysis stage.

COVID-19 Visits

Visits missed due to the COVID-19 pandemic will follow the protocol outlined above for unscheduled/missed visits.

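### Provider consent is scheduled after practices are randomised, with nothing to withhold the allocation, so which providers (and whose patients) enter can depend on the arm

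*Combined protocol and SAP*

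**What the plan says.** Section 7 opens with the order of events: "Prior to any of the following actions, practices will be randomized and EMR changes will be finalized". Under 7.1.1, in the window Day -30 to -1, the first listed action begins "Review the written consent form with the provider". The next is training, whose content depends on the arm.

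Section 5.3 places consent at an extra information session at each practice before the main trial starts: "At this time, informed consent will be obtained from each pediatrician/nurse practitioner participant". It does not say whether that session falls before or after randomisation.

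Section 5.3 also records what was in place beforehand. For practices, "The 18 practices which met the inclusion criteria have provided letters of support". For providers, "A total of 67 providers from the 18 practices to be randomized who met the inclusion criteria will participate in the main trial".

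Section 5.4.2 blinds parents and the staff who do the dental screenings. Providers are not mentioned. Section 4 requires each provider to finish training before enrolling any parent. Section 4.1 names a backup practice that "will be included if needed to replace a practice", without saying up to what point.

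**The concern.** In a cluster trial, randomising practices protects the comparison of the people in them only if their entry does not depend on the allocation. Here providers agree individually, after allocation, and may know the arm. The request also differs by arm. Sections 6.2 and 6.3 give Arm A two 45-minute sessions before the first visit against one in Arm B, plus EMR training and documentation, a scorecard, and three components to be completed satisfactorily before a provider counts as trained.

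A provider who declines is not trained, so that provider's patients would ordinarily not be enrolled. The intention-to-treat set in 12.4 consists of participants who provide the necessary measurements, so it cannot recover children who never entered. Section 5.5.2 covers providers who withdraw after receiving the intervention, but nothing covers refusal between allocation and training. The adjustment variables named in 12.4 do not include prior dental attendance. Any resulting imbalance would be systematic, and longer follow-up would not remove it.

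The backup practice raises a smaller point of the same kind: a practice brought in after allocation would not itself have been randomised.

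**Working it through.** **Order of events**

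| Step | Where | Order relative to randomisation |
|---|---|---|
| Practices' letters of support; 67 providers counted | 5.3 | Before |
| Randomisation; EMR changes finalised | 7 | - |
| Provider signs consent | 7 with 7.1.1 | After |
| Provider consent at information session | 5.3 | Not stated |
| Arm-specific training | 7.1.1 | After |
| Parents recruited | 4 | After |

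Section 7 is explicit and 5.3 does not contradict it. Commitment before allocation therefore exists at practice level and as a list of expected providers, but not as individual signed consent.

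**Precision of the planned comparison**

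Inputs from 12.2: rates 0.46 and 0.30, two-sided 5% test, 80% power, ICC 0.04, 25% dropout, 9 practices per arm.

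1. Without clustering, 144 children per arm are needed.
2. With clustering: 144 × (1 - 0.04) / (1 - 144 × 0.04 / 9) = 138.24 / 0.36 = 384 completers per arm.
3. With dropout: 384 / 0.75 = 512 per arm, which is the plan's figure.
4. Completers per practice: 384 / 9 = 42.67. Design effect: 1 + 41.67 × 0.04 = 2.667. Effective size: 384 / 2.667 = 144 per arm.
5. SE of the difference: √[(0.46 × 0.54 + 0.30 × 0.70) / 144] = 0.056, or 5.6 points. With both arms at 0.30: √(2 × 0.30 × 0.70 / 144) = 0.054.

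**Illustrative size of the bias**

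The documents give no figure for this, so both inputs are assumptions.

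- *f*, the share of one arm's children who would have come from decliners: 6% to 12%. That is about two to four of the 33 to 34 providers in an arm, if children are spread evenly over providers.
- *d*, how far those children's attendance differs from that of the children who do enter: 5 to 15 points.

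The arm's rate with everyone in is *r* - *f* × *d*, and without the decliners' patients it is *r*. The shift is *f* × *d*.

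- Low end: 0.06 × 0.05 = 0.3 points.
- High end: 0.12 × 0.15 = 1.8 points.
- High end against the SE: 1.8 / 5.6 = 0.32. Against the planned effect: 1.8 / 16 = 11%.

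**Consequence at the high end, in each direction**

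- If the shift favours Arm A and there is no true effect, the two-sided error rises from 5% to about 6.3%.
- If the shift goes against Arm A and the true rates are 0.46 and 0.30, power falls from 80% to about 71%.

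At the low end the error stays at 5.0% and power is about 79%. The planned sample size is unaffected, because the issue is bias and not precision.

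**The case against.** The strongest reply is that knowledge of the arm is inferred. Section 7 says practices are randomised first; it does not say that providers are told the result before signing. The EMR change is a weak cue: by 6.2, most University Hospitals practices already hold the oral health questions, hidden until Arm A providers are trained. The practices, which are the randomised units, committed in advance. Eligible providers were counted, and the balance score uses the ratio of patients to providers. All eligible parents are invited and parents are blinded. CME and MOC credits are described without distinction by arm.

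Most of this stands, and it makes the risk small. It does not close it. A list of expected providers is not signed consent, and no section withholds the allocation. The parent-level safeguards do not act on which providers take part.

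A reader might infer more than the documents support:

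- **Refusals have already happened.** Section 4.3 speaks of 63 participating providers against the 67 in 5.3. The 63 relates to interviews held after all third visits, with no reason or arm given, so loss over two years explains it as well as refusal. Section 7.2.5 foresees that "another non-participating provider at the practice is scheduled to see the child", but such a provider could be ineligible, newly hired or withdrawn.
- **Arm A providers alone are observed.** Section 6.3.2 has encounters observed or audiotaped in both arms. Only the scorecard differs.
- **The bias favours the intervention.** That needs decliners to be concentrated in Arm A and their patients to attend less. Nothing in the documents establishes either.
- **An unrandomised practice has been swapped in.** The text merely fails to exclude this. The backup is described together with recruitment of practices before the trial.

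**Conclusion.** The point holds as an open risk. As scheduled, providers consent after their practice is randomised, without stated masking or concealment and with unequal demands by arm. Provider entry, and through it patient entry, can depend on the allocation. No bias has been shown, and its direction is unknown.

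On the assumed ranges the shift is 0.3 to 1.8 points, at most about one third of the standard error. That is too small to create a 16-point effect, but it could matter for a borderline result. The figure rests on the assumed *f* and *d*, on an even spread of children over providers, and on the plan's own ICC and dropout. Taking consent first is standard and cheap, which is why the order is worth changing, or at least documenting, despite the modest size.

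**What to change.** - **Sections 5.3, 7 and 7.1.1:** obtain signed consent from all eligible providers at the 18 practices before the allocation is generated or disclosed to them, and align the three sections on that order.
- **If consent has already been taken:** state whether it preceded disclosure of the allocation. This is the likely case, since the document is Version 9.0 of April 2022 and 7.2.3 already covers re-consent at the third visit on a form dated 12/7/20.
- **Reporting:** give, by arm, the numbers of providers approached, consented, declined and withdrawn before training.
- **Section 4.1:** state that the backup practice may be used only before randomisation; otherwise analyse practices as allocated.

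The cost is small. Practices roll out six at a time over nine months (Section 4), so consent before allocation lengthens the gap to training for later practices, with some turnover possible in between. A practice lost after allocation and not replaced would leave 17 clusters. The reporting items need only a log of provider contacts, and none of the changes affects the sample size.

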7.1 Provider

7.1.1 Baseline Visit: WCV #1

Before WCV #1 (T₋₁: Day -30 to -1)

- Review the written consent form with the provider; study staff signs the consent form acknowledging that informed consent was reviewed and provider signs acknowledging consent was obtained (Appendix C: Consent forms).
- Provide OH didactic education and skills training for pediatricians/nurse practitioners to communicate core OH facts (importance of baby teeth, chronicity of caries, dental visits) to parents/caregivers (Appendix D: Provider training) or AAP based didactic training, based on study arm.
- Administer pre- and post-tests to pediatricians/nurse practitioners before and after the OH didactic education session (Appendix E: Questionnaires & forms).

At WCV #1 (T₀: Day 0)

- Provider delivers oral health facts, based on study arm.
- Provider documents OH in EMR, based on study arm.

7.1.2 Follow-up Visit: WCV #2

Before WCV #2 (T₂: Day 364 ± 90)

- Provide OH didactic education booster session for pediatricians/nurse practitioners.

At WCV #2 (T₃: Day 365 ± 90)

- Provider delivers oral health facts, based on study arm.
- Provider documents OH in EMR, based on study arm (Appendix D: Provider training)

7.1.3 Final Visit: WCV #3

At WCV #3 (T₆: Day 730 ± 90)

- Provider delivers oral health facts, based on study arm.
- Provider documents OH in EMR, based on study arm (Appendix D: Provider training).

After WCV#3 (Day 731 +)

- Revised consent form is reviewed with the provider; study staff signs the consent form acknowledging that informed consent was reviewed and provider signs acknowledging consent was obtained.
- Provider completes structured interview conducted by a trained moderator. The interviews will be conducted at the pediatric practices at a time convenient for the provider. Interviews will be conducted using zoom if in-person interviews are not possible due to the current COVID-19 outbreak. The interviews will contain questions to assess:
 - Relative advantage of the OH intervention
 - Compatibility of the OH intervention with the needs of the adopters
 - Complexity of the OH intervention
 - Trialability
 - Observability
- Provider attends debriefing session held at the practice.

7.1.4 Provider Withdrawal Visit

The following procedures will be followed for providers who choose to withdraw early or whose participation is terminated by the PI:

- Personal contact (by phone or in-person) by study staff will be made to confirm withdrawal.
- Debrief about the interventions.
- If a provider withdraws from the study and their patients are participants who see another provider at that practice, visits and data collection will continue. If the patient also withdraws by changing practices *to a non-participating practice*, visits and data collection will end with these participants being considered lost to follow-up. Data collected up to the point of withdrawal will be used for analysis.

7.2 Parent/Caregiver and Child

7.2.1 Baseline Visit: WCV #1

At WCV #1 (T₀: Day 0)

Before Provider Encounter

- Study Staff will recruit 1024 parent/caregivers and their children from the 18 practices (approximately 56-57 participants/practice) using an in-person approach. Parents/caregivers attending well-child visits with 3-6 year old children will be approached for participation.

- In the waiting area/exam room of the pediatric practice, study staff will review inclusion/exclusion criteria as outlined on the screening survey to determine parent/caregiver and child eligibility (Refer to Sections 5.1, 5.2).
- Review the written consent form with the potential participant; study staff signs the consent form acknowledging that informed consent was reviewed and caregiver signs acknowledging consent was obtained (Appendix C: Consent forms).
- In the waiting area/exam room of the pediatric practice, study staff will obtain contact information.
- In the exam room, caregivers will complete the following self-administered Baseline questionnaires: A1: Illness Perception Questionnaire-Revised for Dental (IPQ-RD) and A2: Parent Questionnaire (Appendix E: Questionnaires & forms).
- In the exam room, dental hygienist will perform child dental screening examination and study staff will record results of the dental screening examination. Results will not be available to the provider, unless the hygienist finds that the child has urgent needs that require immediate attention. (Appendix E: Questionnaires & forms).

During Provider Encounter in the Exam Room

- Caregivers attending WCV's will receive OH information, prescription to take the child to the dentist + list of local Medicaid-accepting dentists from provider, based on study arm.
- Caregivers attending WCV's may have study staff audiotape or directly observe the provider encounter to evaluate provider's delivery of OH communication (for a sample of visits).

After Provider Encounter in the Exam Room/Waiting Area

- Caregivers will provide feedback about the OH information given to them during the medical visit with a short self-administered exit questionnaire (A3: [Appendix E: Questionnaires & forms]).
- Caregivers will be given the B1: Follow-up IPQ-RD (Appendix E: Questionnaires & forms) to be completed and returned (in postage paid envelope or in person, based on participant preference).

After WCV #1 (T₁)

- **B1 (Day 0 ± 120):** Caregivers will receive telephone calls and text messages from study staff to remind them to complete and return the B1: Follow-up IPQ-RD if it has not already been returned.
- **B2 (Day 180 + 60):** Caregivers will receive telephone calls and text messages from study staff 6 months after the WCV to complete the B2: Dental Attendance & Cost Questionnaire (Appendix E: Questionnaires & forms).

7.2.2 Follow-up Visit: WCV #2

At WCV #2 (T₃: Day 365 ± 90)

Before Provider Encounter in the Exam Room

- If a different parent/caregiver brings the child to the well child visit and they are the child's legal guardian, consent will be obtained from that parent/caregiver and they will complete all components of the visit.
- Parent/caregivers will complete the following self-administered questionnaires: A1: Illness Perception Questionnaire-Revised for Dental (IPQ-RD) and A2: Parent Questionnaire.
- Dental hygienist will perform child dental screening examination and study staff will record results of the dental screening examination. Results will not be available to the provider unless the hygienist finds that the child has urgent needs that require immediate attention.

During Provider Encounter in the Exam Room

- Caregivers attending WCV's will receive OH information, prescription to take the child to the dentist + list of local Medicaid-accepting dentists from provider, based on study arm.
- Caregivers attending WCV's may have study staff audiotape or directly observe the provider encounter to evaluate the provider's delivery of OH communication (for a sample of visits).

After Provider Encounter in the Exam Room/Waiting Area

- Caregivers will provide feedback about the OH information given to them during the medical visit using a short self-administered exit questionnaire (A3).
- Parents will be given the B1: Follow-up IPQ-RD to be completed and returned within 2 weeks (in postage paid envelope or in person, based on participant preference).

After WCV #2 (T₄):

- **B1 (Day 365 ± 120):** Caregivers will receive telephone calls and text messages from study staff to remind them to complete and return the B1: Follow-up IPQ-RD if it has not already been returned.
- **B2 (Day 545 ± 90):** Caregivers will receive telephone calls and text messages from study staff 6 months after the WCV to complete the B2: Dental Attendance & Cost Questionnaire (Appendix E: Questionnaires & forms).

